9.6.6 Injection-site assessment

Injection-site assessment data (erythema, induration, categorical pain, pruritus and edema) will be listed and summarized in frequency tables.

9.6.7 Hepatic Safety

If a study patient experiences elevated alanine aminotransferase (ALT) $\geq 3 \times$ upper limit of normal (ULN), alkaline phosphatase (ALP) $\geq 2 \times$ ULN, or elevated total bilirubin (TBL) $\geq 2 \times$ ULN, liver tests (Protocol Appendix 4) should be repeated to confirm the abnormality and to determine if it is increasing or decreasing.

The subjects' liver disease history and associated person liver disease history data will be listed. Any concomitant medication of acetaminophen/paracetamol will be listed. Results from any hepatic monitoring procedures, such as a magnetic resonance elastography scan, and a biopsy assessment will be listed, if performed.

Hepatic risk factor assessment data will be listed. Liver related signs and symptoms data will be summarized by treatment and listed. Alcohol and recreational drug use data will also be listed.

All hepatic chemistry, hematology, coagulation, and serology data will be listed. Values outside the reference ranges will be flagged on the individual subject data listings.

9.6.8 Nasal Inspection

Nasal inspections will be performed for safety monitoring purposes only and will not be presented.

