Injection-Site Assessment Nasal Inspection			Pre-hypoglycemia induction, 90 min Pre-hypoglycemia			Pre-hypoglycemia induction, 90 min Pre-hypoglycemia			Injection-site assessment for IMG only. Nasal inspection both for
Vital Signs	X		induction, 90 min Pre-hypoglycemia			induction, 90 min Pre-hypoglycemia	X		IMG and LY900018. Time points may be
(Supine Blood Pressure, Pulse Rate, and Body Temperature)			induction, Predose, 15, 30, 60, 120, 240 min			induction, Predose, 15, 30, 60, 120, 240 min			added for each period if warranted and agreed upon between Lilly and the investigator. Predose time point will be between insulin infusion stop and study treatment.
Single 12-lead ECG (Local)	X						X		
Triplicate 12-lead ECG (Central)			Pre-hypoglycemia induction (30 and 15 min prior to insulin infusion), Predose, 15, 30, 60, 120, 240 min			Pre-hypoglycemia induction (30 and 15 min prior to insulin infusion), Predose, 15, 30, 60, 120, 240 min			Time points may be added for Period 1 and Period 2 if warranted and agreed upon between Lilly and the investigator. Predose time point will be between insulin infusion stop and study treatment.
Laboratory Tests									
Clinical Serology Tests	X								See Appendix 2, Clinical Laboratory Tests, for details.

	Screening		Period 1	Wash out		Period 2	Follow-up/ED	Additional Follow-up for TE ADA ^a	Comments
Procedure	Days -28 to -2	Day -1	Day 1	3 to 14 days	Day -1	Day 1	Within 28±2 days after last study treatment		
Clinical Lab Tests (Hematology, Clinical Chemistry, and Urinalysis)	X		Pre-hypoglycemia induction			Pre-hypoglycemia induction	X		See Appendix 2, Clinical Laboratory Tests, for details. Patients do not need to fast for samples at screening or follow-up. At Periods 1 and 2, samples should be collected from patients who have fasted at least 8 hours before any study procedures.
HbA1c	X		Pre-hypoglycemia induction						See Appendix 2, Clinical Laboratory Tests, for details.
Pregnancy Test (Female patients of childbearing potential only)	X	X			X		X		Serum pregnancy test will be performed at screening. Urine pregnancy test will be performed at every admission period and follow-up visit if applicable.
FSH (Female patients only)	X								When needed to confirm postmenopausal status.
Ethanol Testing	X								Additional tests can be done at the discretion of the investigator.

	Screening		Period 1	Wash out		Period 2	Follow-up/ED	Additional Follow-up for TE ADA ^a	Comments

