9.5.4. Other Tests

Nasal inspections with nasal speculum and injection-site assessments will be conducted according to the Schedule of Activities (Section 2). This inspection will ascertain whether sites are normal in appearance prior to and after drug administration.

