4.2 Secondary

The secondary objectives are:

- To compare the safety and tolerability of 3 mg LY900018 with 1 mg IMG
- To characterize the PK profile of 3 mg LY900018 compared to 1 mg IMG
- To characterize the PD profile of 3 mg LY900018 compared to 1 mg IMG

Final, 01 Feb 2018 Page 6 of 26

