9. STATISTICAL METHODOLOGY

9.1 General

Data listings will be provided for all data that is databased. Summary statistics and statistical analysis will only be presented for data where detailed in this SAP. For continuous data, summary statistics will include the arithmetic mean, arithmetic standard deviation (SD), median, minimum (and/or 1st quartile), maximum (and/or 3rd quartile) and N; for log-normal data (e.g. the PK parameters: area under the concentration versus time curve [AUCs] and the maximum observed drug concentration [C_{max}]) the geometric mean and geometric coefficient of variation (CV%) will also be presented. For categorical data, frequency count and percentages will be presented. Data listings will be provided for all subjects up to the point of withdrawal, with any subjects excluded from the relevant population highlighted. Summary statistics and statistical analyses will generally only be performed for subjects included in the relevant analysis population. For the calculation of summary statistics and statistical analysis, unrounded data will be used.

Mean change from baseline is the mean of all individual subjects' change from baseline values. Each individual change from baseline will be calculated by subtracting the individual subject's baseline value from the value at the timepoint. The individual subject's change from baseline values will be used to calculate the mean change from baseline using a SAS procedure such as Proc Univariate.

As the study includes T1DM and T2DM patients, the following parameters will be reported by diabetes type and the results will be included in (but not limited to) the summary report:

Final, 01 Feb 2018 Page 9 of 26

- Subject Disposition
- Demographics
- Proportion of Treatment Success
- PK parameters
- PD parameters
- Plasma Glucose values over time
- Adverse events
- Hypoglycemia

Data analysis will be performed using SAS® Version 9.4 or greater.

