9.6 Safety and Tolerability Assessments

9.6.1 Adverse events

Where changes in severity are recorded in the Case Report Form (CRF), each separate severity of the AE will be reported in the listings, only the most severe will be used in the summary tables. A pre-existing condition is defined as an AE that starts before the subject has provided written informed consent and is ongoing at consent. A non-treatment emergent AE is defined as an AE which starts after informed consent but prior to dosing. A treatment-emergent AE is defined as an AE which occurs postdose or which is present prior to dosing and becomes more severe postdose.

All AEs will be listed. Treatment-emergent AEs will be summarized by diabetic type, treatment, severity and relationship to the study drug. The frequency (the number of AEs, the number of subjects experiencing an AE and the percentage of subjects experiencing an AE) of treatment-emergent AEs will be summarized by treatment, Medical Dictionary for Regulatory Activities (MedDRA) version 20.1 system organ class and preferred term. The summary and frequency AE tables will be presented for all causalities and those considered related to the study drug. Any serious AEs will be tabulated.

Nasal/respiratory/anosmia AEs will be identified using MedDRA preferred term (see Appendix 1 for the list of preferred terms) and summarized by treatment group. The frequency (the number of AEs, the number of patients experiencing an AE, and the percentage of patients experiencing an AE) of nasal/respiratory/anosmia TEAEs for each preferred term will be summarized by treatment.

The time needed for resolution of nasal/respiratory/anosmia AEs will be calculated based on the start and end date/time reported by the investigator and summarized using descriptive statistics. Events that did not resolve will be excluded from calculation of the time to resolution. This analysis will include all AEs (ie, patients experiencing AEs with the same preferred term at different time points will be counted multiple times).

Kaplan-Meier curve for each treatment will be produced for time to resolution of nasal/respiratory/anosmia AEs. If the event did not resolve during the study, then it will be treated as censored observation at the end of the study.

Clinically significant abnormal findings through electrocardiograms (ECGs), nasal inspection, injection site inspection, and physical examination will be captured as AEs.

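### Nasal inspection results are neither listed nor tabulated, unlike the comparator's injection-site results, so nasal findings below clinical significance and the normal/abnormal rate go unreported

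*SAP*

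**What the plan says.** **Collection.** The Schedule of Activities (Protocol Section 2) places nasal inspection before hypoglycemia induction and at 90 minutes in each period. Its comment column reads "Injection-site assessment for IMG only. Nasal inspection both for" and goes on to name both treatments. Protocol 9.5.4 describes nasal speculum inspection and injection-site assessment together and gives them one purpose: "This inspection will ascertain whether sites are normal in appearance prior to and after drug administration".

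**Reporting.** The SAP separates the two sites.
- Nose (SAP 9.6.8): "Nasal inspections will be performed for safety monitoring purposes only and will not be presented".
- Injection site (SAP 9.6.6): "Injection-site assessment data (erythema, induration, categorical pain, pruritus and edema) will be listed and summarized in frequency tables".

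**Related rules.**
- SAP 9.6.1 brings the more important findings from either site into the AE data: "Clinically significant abnormal findings through electrocardiograms (ECGs), nasal inspection, injection site inspection, and physical examination will be captured as AEs".
- SAP 9.1 sets the general default: "Data listings will be provided for all data that is databased".
- SAP 9.6.13 says that safety assessments not otherwise detailed are at least listed.
- A secondary objective (SAP 4.2) is "To compare the safety and tolerability of 3 mg LY900018 with 1 mg IMG".

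**The concern.** The product under test is given through the nose, and Protocol 3.3 names nasal symptoms among its risks. The study already pays for a before-and-after look at the nose under each treatment. Each patient therefore has a pre-dose reference in each period and, in the IMG period, a within-patient control. The SAP then withholds the results of that look, while showing the corresponding results for the comparator's site.

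The reason given is that the inspections serve safety monitoring only. Protocol 9.5.4 gives injection-site assessment the same purpose, and those results are tabulated.

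At stake is a modest but relevant part of the tolerability comparison. A reader of the study report could not see how often the nasal cavity looked abnormal after LY900018, how often it looked abnormal after IMG in the same patients, or whether changes short of clinical significance occurred at all.

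**Working it through.** No figure in the plan bears on this point, so there is none to reproduce. The check compares the reporting routes, then counts what is missing.

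**1. What is reported for each site**

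| Item | Nose | Injection site |
|---|---|---|
| Scheduled (Protocol Section 2) | Both treatments, pre-induction and 90 min | IMG only, pre-induction and 90 min |
| Clinically significant findings | AEs (SAP 9.6.1) | AEs (SAP 9.6.1) |
| Dedicated AE summary | Yes: nasal/respiratory/anosmia terms by treatment, with time to resolution | None specified |
| Patient questionnaire | Yes (SAP 9.6.10) | None specified |
| Assessment results themselves | Not presented (SAP 9.6.8) | "will be listed and summarized in frequency tables" (SAP 9.6.6) |

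The two sites share the AE rule. That rule therefore cannot explain why the underlying results are withheld for one site only.

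**2. Whether the other nasal outputs fill the gap**
- *AE tables.* The term list in SAP Appendix 1 includes objective findings such as mucosal erosion, ulcer, oedema, crusting and septum perforation. An inspection finding enters by this rule only once it is judged clinically significant. The tables also do not show how many inspections were normal.
- *Questionnaire.* Its nine items (Protocol Appendix 6) are symptoms of the nose, eyes, ears and throat, reported by the patient. None records the appearance of the mucosa.

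Two things have no route into the report: findings below clinical significance, and the normal/abnormal rate after each treatment.

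**3. How many inspections this concerns**

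Inputs: up to 75 enrolled and at least 66 completers (SAP Section 7); 2 periods; 2 time points per period (Protocol Section 2).
- All inspections: 75 × 2 × 2 = 300, or 66 × 2 × 2 = 264 for completers alone.
- Post-dose inspections on LY900018: one per patient, so 66 to 75. The same number follows IMG.

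**4. What a clean result could have shown**

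With zero new abnormalities in *n* inspections, the upper limit of the two-sided 95% exact interval is 1 − 0.025^(1/*n*). The one-sided 95% limit is 1 − 0.05^(1/*n*).

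| *n* | Two-sided 95% upper limit | One-sided 95% upper limit |
|---|---|---|
| 66 | 5.4% | 4.4% |
| 75 | 4.8% | 3.9% |

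These limits are an illustration, not a forecast. They assume no events, one usable post-LY900018 inspection per patient, and a normal nose before induction. A patient already abnormal at that point would drop out of the denominator.

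**The case against.** **Nasal tolerability is well covered elsewhere.** This is largely right. Clinically significant inspection findings reach the AE tables, nasal AEs get their own summary by treatment with Kaplan-Meier curves for resolution, and the questionnaire is compared by a repeated-measures model with category shifts. A reader of SAP 9.6.8 alone might infer that all inspection findings are discarded, or that local nasal safety is left out of the comparison. The documents do not support that. In these respects the nose is analysed more fully than the injection site.

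**No commitment is broken.** This also stands. The protocol's safety endpoints are SAEs, TEAEs (including nasal AEs) and vital signs, and Protocol 10.3.2 promises no summary of inspections. However, it does not promise one of injection-site assessments either, and the SAP tabulates those.

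**SAP 9.1 is not necessarily contradicted.** A reader might see a direct conflict with the rule that all databased data are listed. The conflict exists only if inspection results are databased, which neither document says, and a specific section would ordinarily override a general one. What remains is that 9.6.8 puts the nose below the listing default of SAP 9.6.13.

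**The inspection is open-label too.** Correct. Protocol 7.3 withholds the allocation list only from those who assess treatment response or decide on additional action to raise glucose. An inspection table would be no better protected from bias than the AEs or the questionnaire. It would add a different kind of observation, not a blinded one.

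**One look at 90 minutes may miss short-lived effects.** It may, but that limits what the result can show and is not a reason to withhold it.

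**Supplementary analyses are allowed.** SAP Section 3 permits them, but it does not commit anyone to this one, and 9.6.8 says the opposite.

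**Conclusion.** The point holds in a narrow form. SAP 9.6.8 is an explicit rule, so this is not a matter of missing detail. The rule withholds the results of 66 to 75 post-LY900018 inspections and as many after IMG, while the IMG injection-site results are shown. The loss is confined to nasal findings judged not clinically significant and to the normal/abnormal rate by treatment. For scale, a result with no new abnormalities would have bounded that rate at about 5.4% (66 patients) to 4.8% (75 patients), two-sided 95%, under the assumptions listed with the calculation. For clinically significant findings, the nasal AE tables already allow a comparable statement.

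The primary analysis is unaffected, and no protocol-specified analysis is missing. The change is still worth making. It serves the secondary tolerability objective for the test product's own route of administration, uses procedures already scheduled, and removes a difference between the two sites for which the documents give no distinguishing reason.

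**What to change.** Replace the text of SAP 9.6.8 with wording to this effect: *Nasal inspection results (normal/abnormal, with a description of any abnormality) will be listed by patient, period and time point. The shift from pre-induction to 90 minutes postdose will be summarised by treatment in frequency tables, as for injection-site assessments. New abnormalities after LY900018 will be shown beside those after IMG in the same patients.*

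The SAP should also state whether inspection results are databased. If they are not, one normal/abnormal field with a free-text description has to be added to the CRF.

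Cost: one listing, one shift table and possibly that one field; no new procedure or visit. The table should be labelled descriptive, because the inspection is open-label and SAP 9.6.14 plans no inferential safety analyses. If the sponsor prefers to keep the omission, the SAP should say why the nose is handled differently from the injection site. That would explain the difference but would not recover the information.

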9.6.9 Hypoglycemic episodes

Hypoglycemic event data will be listed and summarized by hypoglycemia category, treatment and diabetes type as defined in the Protocol (Section 9.5.5.1).

Severe hypoglycemic events will be reported separately as SAEs.

Final, 01 Feb 2018 Page 21 of 26

9.6.10 Nasal and Non-nasal Score Questionnaire

The scoring for each response to the Nasal and Non-Nasal Score Questionnaire will follow the scale displayed on the questionnaire ('None'=0, 'Mild'=1, 'Moderate'=2, 'Severe'=3). The total score of the questionnaire will be calculated as the sum of the scores for each question. Descriptive statistics will be used to summarize the baseline, various postdose time points (15, 30, 60, and 90 minutes), and absolute change from baseline in total score of Nasal and Non-Nasal Score Questionnaire by treatment group.

For this analysis, baseline is defined as the score measured prior to glucagon administration at each treatment visit.

The total score will be compared between treatment groups through a linear MMRM that accounts for the correlation due to the crossover design and the correlation due to repeated measures of the questionnaire. The MMRM analysis of nasal symptom score will be performed using the similar approach as specified in the plasma glucose analysis.

The number and proportion of patients within each score categories of each question in the Nasal and Non-Nasal Score Questionnaire in increasing severity (none, mild, moderate, and severe) at each time point and shift of categories from baseline to maximal (and last) postdose severity category will be provided by treatment group.

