Procedure	Days -28 to -2	Day -1	Day 1	3 to 14 days	Day -1	Day 1	Within 28±2 days after last study treatment		
Urine Drug Screen	X								Additional tests can be done at the discretion of the investigator.
PK (Glucagon)			Pre-hypoglycemia induction, Predose, 5, 10, 15, 20, 25, 30, 40, 50, 60, 90, 120, 240 min			Pre-hypoglycemia induction, Predose, 5, 10, 15, 20, 25, 30, 40, 50, 60, 90, 120, 240 min	X	X	Sampling times are relative to the time of study treatment administration (0 min). Predose time point will be between insulin infusion stop and study treatment.
Plasma Glucose for PD			Pre-hypoglycemia induction, -5, Predose, 5, 10, 15, 20, 25, 30, 40, 50, 60, 90, 120, 240 min			Pre-hypoglycemia induction, -5, Predose, 5, 10, 15, 20, 25, 30, 40, 50, 60, 90, 120, 240 min			-5 mins = stop insulin infusion. Sampling times are relative to the time of study treatment administration (0 min). Predose time point will be between insulin infusion stop and study treatment.
Genetic Sample (Stored)		X							Single sample for pharmacogenetic analysis taken prior to/on Period 1 Day -1.

	Screening		Period 1	Wash out		Period 2	Follow-up/ED	Additional Follow-up for TE ADA ^a	Comments
Procedure	Days -28 to -2	Day -1	Day 1	3 to 14 days	Day -1	Day 1	Within 28±2 days after last study treatment		
Anti-glucagon Antibodies			Pre-hypoglycemia induction				X	X	In the event of drug hypersensitivity reactions (immediate or non-immediate), samples will be collected as close to event onset as possible, at event resolution, and 30 days following the event. Patients with TE ADA at follow-up/ED will undergo additional follow-up. Refer to Section 9.7.1 for details.
Health Outcome Instruments									
Clarke Hypoglycemia Awareness Survey		X							
Nasal and Non-nasal Score Questionnaire			Pre-hypoglycemia induction, 15, 30, 60, 120 min			Pre-hypoglycemia induction, 15, 30, 60, 120 min			Sampling times are relative to the time of study treatment administration (0 min). Questionnaire will be collected in both LY900018 and IMG treatment groups in both periods.

	Screening		Period 1	Wash out		Period 2	Follow-up/ED	Additional Follow-up for TE ADA ^a	Comments
Procedure	Days -28 to -2	Day -1	Day 1	3 to 14 days	Day -1	Day 1	Within 28±2 days after last study treatment		

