9.2.3. Post Glucagon Administration

For 120 minutes after glucagon administration, bedside PG levels will be measured no more than 5 minutes apart when the PG is <90 mg/dL, and no more than 10 minutes apart when PG is ≥90 mg/dL using a glucose analyzer (Antsense Duo, HORIBA Ltd. or equivalent).

Blood samples will be collected at predose and various time points post glucagon administration for PG (PD, as measured by central laboratory) and/or glucagon (PK) measurements according to the Schedule of Activities (Section 2).

To accurately capture the PG profile, the site should not give patients any calorie-containing food/drink within 90 minutes of glucagon administration unless there is a safety concern.

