Appendix 5. Blood Sampling Summary

This table summarizes the approximate number of venipunctures and blood volumes for all blood sampling (screening, safety laboratories, and bioanalytical assays) during the study.

Protocol I8R-JE-IGBJ Sampling Summary

Purpose	Blood Volume per Sample (mL)	Number of Blood Samples	Total Volume (mL)
Screening testsa,b	27	1	27
Clinical laboratory testsa	9	3	27
Safety glucose monitoring ^c	1	140d	140
Pharmacokinetics (Glucagon)	4	32e,f	128
Pharmacodynamics (Plasma Glucose)	2	30	60
HbA1c (Period 1)	2	1	2
Anti-glucagon antibody	5	2 ^e	10
Pharmacogenetics	5	1	5
Total			399

- a Additional samples may be drawn if needed for safety purposes.
- b Because screening tests are performed at local laboratories at each site, this volume is an estimate and will vary depending on the local laboratory's testing requirements.
- ^c Sample volume may vary by each clinical research unit. The number of samples may vary by each patient.
- d Number of samples for safety glucose monitoring calculated assuming samples are collected approximately every 3 minutes for 90 minutes during hypoglycemia induction. Samples collected for 90 minutes + 120 minutes post glucagon dose = 210 minutes per period/3 = 70 samples per period × 2 periods = 140 samples total.
- e Samples for immunogenicity should be collected every 12 weeks until the titer returns to baseline (ie, returns to within a single 2-fold dilution of the baseline titer) or until 1 year after the last dose of study treatment. A time-matched pharmacokinetics (glucagon) sample may be collected at the follow-up immunogenicity assessment(s) if warranted and agreed upon between both the investigator and sponsor.
- f Includes 3 additional samples to be drawn if needed.

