9.5.3 Plasma Glucose Values Statistical Methodology

Descriptive statistics will be used to summarize the baseline, various postdose time points (15, 30, 45, 60, and 90 minutes post glucagon administration), and absolute change from baseline in PG values by treatment group for the FAS.

If a patient receives additional intervention to raise PG concentrations, measurements taken after the time of intervention will be excluded from the analysis.

For this analysis, baseline is defined as the last nonmissing PG measured at the time of or immediately prior to glucagon administration at each treatment visit. A treatment comparison of glucose over the 90 minutes following administration of glucagon will be completed using a linear mixed model with repeated measures (MMRM) that accounts for the correlation due to the crossover design and the correlation due to multiple measures. The baseline score, treatment period, time points and their interaction will be included as covariates in the model. Least-square means and 2-sided 95% confidence limits will be calculated for the difference in PG between treatment groups (IMG minus NG) at each time point.

In the MMRM model, the within-patient errors are modelled as an unstructured variance-covariance matrix. If the analysis fails to converge, the following variance-covariance matrix will be used (in the order listed) until one converges:

- 1. Heterogeneous Toeplitz (TOEPH)
- 2. Heterogeneous First-order Autoregressive (ARH[1])
- 3. Heterogeneous Compound Symmetry (CSH)
- 4. Toeplitz (TOEP)
- 5. First-order Autoregressive (AR[1])
- 6. Compound Symmetry (CS)

The Kenward-Roger approximation will be used to estimate denominator degrees of freedom for the MMRM models.

Below is the example SAS code performing the MMRM analysis:

```
proc mixed data=c;
class patient time visit treatment;
model value = treatment time visit baseline treatment*time /solution
ddfm=kr;
repeated time(visit)/subject=patient type=un;
lsmeans treatment*time/cl diff om;
run;
```

As an exploratory analysis and if there is sufficient data, a subgroup analysis of plasma glucose over time by concomitant oral diabetes drug will be performed (with particular focus on Sulfonylureas). The purpose of the analysis is to assess whether the concomitant oral diabetes

Final, 01 Feb 2018 Page 18 of 26

drug triggers rebound hypoglycaemia or not. For each concomitant oral diabetes drug, the data will be summarized by treatment and diabetes type.

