9.6.11 Edinburgh Hypoglycemia Scale: Experimental Hypoglycemia

The Edinburgh Hypoglycemia Scale data will be analyzed in the same way as the nasal questionnaire data for the ARS.

If a patient receives rescue treatment to raise PG concentrations, measurements taken after the rescue will be excluded from the analysis.

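### SAP 9.6.10 summarises the nasal questionnaire total score at 90 minutes, when it is not collected, and omits 120 minutes, when it is; separately, SAP 9.5.3 lists plasma glucose at an unscheduled 45 minutes.

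*SAP*

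**What the plan says.** **Questionnaire totals.** SAP 9.6.10 sums the item scores and describes the total, and its change from baseline, at "various postdose time points (15, 30, 60, and 90 minutes". It then plans a repeated-measures mixed model of the total, by-question category counts at each time point, and shift tables to the maximal and last postdose category. Section 2 of the protocol (Schedule of Activities) collects the questionnaire in each period at "Pre-hypoglycemia induction, 15, 30, 60, 120 min".

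**Edinburgh scale.** SAP 9.6.11 gives no times of its own. It says: "The Edinburgh Hypoglycemia Scale data will be analyzed in the same way as the nasal questionnaire data for the ARS". The Schedule of Activities places this scale postdose at 15, 30, 60 and 120 minutes, with further assessments before dosing.

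**Plasma glucose.** SAP 9.5.3 summarises glucose at "various postdose time points (15, 30, 45, 60, and 90 minutes post glucagon administration". The schedule row for pharmacodynamic glucose reads "Pre-hypoglycemia induction, -5, Predose, 5, 10, 15, 20, 25, 30, 40, 50, 60, 90, 120, 240 min". Protocol 9.2.3 sends those samples to the central laboratory: "Blood samples will be collected at predose and various time points post glucagon administration for PG (PD, as measured by central laboratory".

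**The concern.** A list of summary times should match the times at which data exist. SAP 9.1 confines summary statistics to what the SAP details, so a closed list of times acts as an instruction. For vital signs and ECGs (9.6.4 and 9.6.5) the SAP instead asks for every timepoint, so the short list in 9.6.10 cannot be read as shorthand for all collected times.

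The question at stake is whether nasal and related symptoms have settled by the last assessment. Protocol 9.3.1.2 has non-serious events elicited by the questionnaire recorded and analysed separately, and only serious ones entered as adverse events. The adverse event tables therefore do not duplicate the score. If the 120-minute total is dropped, the summary shows nothing after 60 minutes, while the shift to the last category in the same section would naturally be taken from 120 minutes. For the Edinburgh scale, recovery from symptoms is itself an exploratory objective.

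**Working it through.** **1. Reproduce the plan's own count.** Appendix 5 of the protocol, in its row "Pharmacodynamics (Plasma Glucose", gives 30 samples per patient. The schedule has 3 glucose samples up to dosing (pre-induction, -5, predose) and 12 after it (5, 10, 15, 20, 25, 30, 40, 50, 60, 90, 120, 240):

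3 + 12 = 15 per period; 15 x 2 periods = 30, as stated.

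A 45-minute draw would give 16 x 2 = 32, which does not match. The schedule row is therefore complete, and no central-laboratory sample is planned at 45 minutes. The same method reproduces the glucagon count: 14 x 2 + 1 at follow-up + 3 optional = 32, as stated.

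**2. Compare the lists in both directions** (minutes after dosing):

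| Output | SAP list | Scheduled | Listed, not scheduled | Scheduled, not listed |
|---|---|---|---|---|
| Nasal total score (9.6.10) | 15, 30, 60, 90 | 15, 30, 60, 120 | 90 | 120 |
| Edinburgh total score (9.6.11, if the list carries over) | 15, 30, 60, 90 | 15, 30, 60, 120 | 90 | 120 |
| Plasma glucose (9.5.3) | 15, 30, 45, 60, 90 | the 12 times in step 1 | 45 | 5, 10, 20, 25, 40, 50, 120, 240 |

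The last cell is not a fault in itself. A summary may use selected times, and 9.5.3 is aimed at the first 90 minutes. Only 45 is a mismatch.

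**3. Size.**
- Nasal total score: 1 of 4 listed times has no scheduled score, and 1 of 4 collected postdose times is omitted. The summary covers 3 of 4 and ends at 60 of 120 minutes.
- Edinburgh total score: the same figures, on the condition stated.
- Glucose: 1 of 5 listed times has no scheduled central-laboratory value. The nearest draws are at 40 and 50.

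**4. Reach.** Treatment success uses central-laboratory glucose up to 30 minutes after dosing. The postdose samples in that window (5, 10, 15, 20, 25, 30) are all scheduled, so the primary outcome does not depend on any of the mismatched times.

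**The case against.** **The 120-minute scores survive elsewhere.** This stands in part. They remain in the listings and, on a natural reading, in the by-question and shift tables, because 9.6.10 builds those at each time point and to the last category. A reader might infer that the 120-minute data are lost altogether; the documents do not support that. What is lost is the total-score summary at that time, and the model estimate if the model uses the same list. SAP 9.6.14 says that no inferential safety analyses are planned, so the point rests on the descriptive summary.

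**The Edinburgh scale may not inherit the list.** This also stands. Analysis in the same way cannot be wholly literal, since the nasal items are scored 0 to 3 and the 13 Edinburgh items 1 to 7. Using the nasal method at the Edinburgh scale's own scheduled times is a fair reading, so this part is conditional.

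**Bedside glucose could fill the 45-minute row.** Possibly. After dosing, "bedside PG levels will be measured no more than 5 minutes apart when the PG is <90 mg/dL", with a wider interval above that level. Protocol 9.2.4 refers to a bedside value at 45 minutes, and the explicit central-laboratory restriction in the SAP concerns treatment success. But the schedule labels bedside glucose as safety monitoring, 9.2.3 sets maximum intervals rather than fixed clock times, and SAP 9.5.3 does not name it as the source. A reader might infer that glucose data between 30 and 60 minutes go unreported. They do not: SAP 9.5.1 summarises individual concentrations by treatment, which can take in the 40- and 50-minute values.

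**The glucose mixed model.** A reader might infer that it must be respecified. SAP 9.5.3 does not tie the model to the descriptive list, so this does not follow. If it did use that list with 45 unavailable, an unstructured matrix over 4 times x 2 visits (k = 8) would have 8 x 9 / 2 = 36 parameters. Adding both 40 and 50 would give k = 12 and 12 x 13 / 2 = 78. That enlargement goes beyond correcting the mismatch.

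**SAP section 11.** A reader might infer that its statement of no changes from the protocol analyses is false. Protocol 10.3.1.2.1, 10.3.1.3.1 and 10.3.2.2 name no analysis times, so the conflict is with the collection schedule only.

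**Conclusion.** Wrong as written, and minor. For the nasal questionnaire the mismatch is plain: a 90-minute row that cannot be filled from scheduled data, and a collected 120-minute total score left out. For the Edinburgh scale the same holds if 9.6.11 carries the time list over. The 45-minute glucose entry needs reconciling but costs no collected data.

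The conclusion assumes that the SAP lists are followed literally. The table shells are a separate document not available here and may already use the collected times. The questionnaire score supports the secondary safety and tolerability objective but is not itself named in the endpoint table; the Edinburgh scale serves an exploratory objective. The primary test, power and sample size are unaffected.

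**What to change.** - **SAP 9.6.10, and for 9.6.11:** use 15, 30, 60 and 120 minutes for the total-score summary and for any mixed model of the total score. Stating the times in 9.6.11 removes the doubt about the cross-reference.
- **SAP 9.5.3:** reconcile the glucose list with the schedule by removing 45 or replacing it with a scheduled time (40 and/or 50). The specification of the glucose mixed model need not change.
- **Table shells:** check that they match.

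The cost is a few words in the SAP and matching shell edits. No new data are needed, and the questionnaire list stays at four times.
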